### 9.3.2. Contra-indications and new indications

#### CONTRA-INDICATIONS

- History of Ischemic heart disease (IHD): myocardial infarction, angina pectoris, coronary artery bypass surgery (diagnoses or nitrate use) in year prior to SR therapy initiation.
- History of Peripheral arterial disease (PAD) in year prior to SR therapy initiation.
- History of transient ischemic attack (TIA) or stroke (ischemic or haemorrhagic) in year prior to SR therapy initiation.
- Uncontrolled hypertension, defined by MAH as the combination of the following: 1.previous diagnosis of hypertension coded in electronic medical records; 2.documented use of any anti-hypertensive therapy (either at that time or in the previous year before SR therapy initiation); and 3. at least two readings of Systolic Blood Pressure  $\geq 150$  or Diastolic Blood Pressure  $\geq 95$  mmHg recorded in the 3 months prior to SR therapy initiation.
- History of thromboembolic events (pulmonary embolism and deep venous thrombosis) in year prior to SR therapy initiation.

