### 7.2. Regulatory action

In the frame of 13th PSUR assessment, data submitted raised concern regarding cardiovascular safety beyond the already recognized risk for venous thromboembolism. Analysis of pooled data from randomized studies in around 7,500 post-menopausal women with osteoporosis showed an increased risk of myocardial infarction with Protelos/Osseor as compared with placebo (1.7% versus 1.1 %), with a relative risk of 1.6 (95% CI, 1.07 to 2.38), and an increased risk of venous thrombotic and embolic events — 1.9% versus 1.3 % with a relative risk of 1.5 (95% CI, 1.04 to 2.19).

As a result of this assessment, an increased risk for serious cardiac disorders, including myocardial infarction has been identified and risk minimization measures specifically targeting this identified risk were recommended by the CHMP. These risk minimization measures included a restriction of the target population by excluding patients with established, current or past history of ischaemic heart disease, peripheral arterial disease and/or cerebrovascular disease and/or uncontrolled hypertension, and restricting the indication to severe osteoporosis in postmenopausal women at high risk for fracture to reduce the risk of vertebral and hip fractures and the treatment of severe osteoporosis in adult men at increased risk of fracture. Patients with significant risk factors for cardiovascular events (e.g. hypertension, hyperlipidaemia, diabetes mellitus and smoking) should only be treated with strontium ranelate after careful consideration. In addition, strontium ranelate therapy should only be initiated by a physician with experience in the treatment of osteoporosis. These changes were disseminated in the form of a DHPC in May 2013.

In view of this newly identified risk of serious cardiac disorders, an overall benefit/risk review under Article 20 of regulation (EC) No 726/2004 started in May 2013 and was finalized on 20 February 2014 ([EMA/112925/2014, 2014](#)). This led to a restriction of the indication to patients (postmenopausal women and men) with severe osteoporosis at high risk of fracture for whom treatment with other medicinal products approved for the treatment of osteoporosis is not possible due to, for example, contraindications or intolerance. As part of RMM, a new DHPC was disseminated in March 2014.

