### 9.2.5.3. Comparative safety study

Patients with any of the newly defined contra-indications will be excluded:

1. Established, current or past history of ischemic heart disease (IHD),
2. Peripheral arterial disease (PAD),
3. Cerebrovascular disease (CVD),
4. Uncontrolled hypertension, defined by MAH using an operational definition as follows: a patient will be defined as 'uncontrolled hypertension' if the 3 following conditions apply:
  - a. There is a previous diagnosis of hypertension coded in electronic medical records.
  - b. There is documented use of any anti-hypertensive therapy (either at that time or in the previous year before SR/BP initiation).
  - c. There are at least two readings of Systolic Blood Pressure  $\geq 150$  or Diastolic Blood Pressure  $\geq 95$  mmHg recorded in the 3 months prior to SR/BP initiation.

Also, eligible patients with a diagnosis of Paget's disease of bones will be excluded. And for the outcome VTE we will exclude patients with a previous VTE.

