## Confounding

Due to the observational design chosen, causality in the observed associations will not be established. Instead, associations between drug use and risks will be assessed. As confounding by indication (with SR patients most likely to suffer more severe osteoporosis) will likely produce differences between SR and bisphosphonate users, especially after the different DHPCs, we will use several methods to deal with between-person confounding:

1. Restriction: comparative studies will be conducted only in persons without contra-indications to restrict the population to those that would be prescribed SR according to the new label.
2. Matching: for the comparative studies we will match cases to controls on age, sex, date, country.
3. Adjustments: we will adjust for all co-variables that are associated with a 10% change in the primary risk estimate.

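### Section 9.3.2 counts a contraindication only if recorded in the year before SR initiation, narrower than the restriction being evaluated, and 9.2.5.3 leaves prior VTE in two of the three comparisons

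*Protocol*

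**What the plan says.** Section 7.2 (and the abstract) describes the measure under evaluation as "excluding patients with established, current or past history of ischaemic heart disease, peripheral arterial disease and/or cerebrovascular disease", with no time limit.

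Section 9.3.2 defines the contraindications as study variables, all but uncontrolled hypertension with a one-year window:

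- IHD: "myocardial infarction, angina pectoris, coronary artery bypass surgery (diagnoses or nitrate use) in year prior to SR therapy initiation"
- PAD: "History of Peripheral arterial disease (PAD) in year prior to SR therapy initiation"
- Cerebrovascular disease: "History of transient ischemic attack (TIA) or stroke (ischemic or haemorrhagic) in year prior to SR therapy initiation"
- VTE: "History of thromboembolic events (pulmonary embolism and deep venous thrombosis) in year prior to SR therapy initiation"

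Section 9.2.5.3, the exclusion list for the comparative safety study, words IHD as "Established, current or past history of ischemic heart disease (IHD" and lists PAD and CVD with no window. VTE is not in that list. It appears only in a closing sentence: "for the outcome VTE we will exclude patients with a previous VTE".

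The abstract lists VTE among the contraindications. The abstract's safety analysis, safety objective 2 in section 8, and section 9.9 all limit the comparison to people free of contraindications; 9.9 says "comparative studies will be conducted only in persons without contra-indications".

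**The concern.** The RMM study asks whether prescribers stopped giving SR to people with a history of cardiovascular disease. Under 9.3.2, a patient whose stroke was two years earlier and who has no later code is scored as having no contraindication, although the restriction covers that patient. The error therefore favours apparent compliance.

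Two results are affected. One is the prevalence for RMM objective 2, together with the interrupted time series built on it (9.7.2.2). The other is the safety incidence rates stratified by number of contraindications at cohort entry (9.7.3.2), where a user with only older disease falls into the zero stratum.

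The VTE point is separate. The comparative population is described as free of contraindications, but for two of the three endpoints it still includes people with a condition that the protocol calls a contraindication.

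**Working it through.** **Rules side by side**

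| Condition | 7.2 / abstract | 9.3.2 | 9.2.5.3 |
|---|---|---|---|
| IHD | current or past | prior year | current or past |
| PAD, CVD | current or past | prior year | no window |
| VTE | contraindication in the abstract, no window | prior year | any previous VTE, VTE outcome only |
| Uncontrolled hypertension | listed | own rule | same rule as 9.3.2 |

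Only uncontrolled hypertension agrees across 9.3.2 and 9.2.5.3. For VTE, the one-year window conflicts with 9.2.5.3 and sits beside an unwindowed entry in the abstract. The restriction quoted from 7.2 concerns IHD, PAD and CVD.

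**Longer look-back is already used.** The same section 9.3.2 uses all available time before SR for fracture history, earlier osteoporosis drugs and bisphosphonate contraindications. Appendix 14.3.2 stars codes such as old MI and history of stroke for baseline use. Under a one-year window these help only if entered within that year.

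**Prevalent users.** The window is anchored on SR initiation. Section 9.7.2.1 says the duration of use is unknown for prevalent users, yet prevalence is also estimated for them.

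**The plan's own figures (9.5.1, 9.5.2)**

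n = 1.96² × p(1−p) / 0.05²

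- Men, p = 0.295: 319.6, rounded up to 320, as stated.
- Women, p = 0.192: 238.4, rounded up to 239, as stated.
- Eligible SR users: 31,500 × [1 − (0.9 × 0.192 + 0.1 × 0.295)] = 31,500 × 0.7977 = 25,128, as stated.

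These figures are sound.

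**Effect of the one-year rule.** Let p be the any-history prevalence and f the share of those patients who also have a record in the last year. Measured prevalence is f × p and the shortfall is (1−f) × p. The protocol gives no f. It also does not say what look-back lies behind 19.2% and 29.5%; here they are taken as any-history values.

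| f (assumed) | Women, f × 19.2% | Men, f × 29.5% |
|---|---|---|
| 1.0 | 19.2% | 29.5% |
| 0.7 | 13.4% | 20.7% |
| 0.5 | 9.6% | 14.8% |
| 0.3 | 5.8% | 8.9% |

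The shortfall exceeds the planned precision of ±0.05 once f is below 1 − 0.05/0.192 = 0.74 in women or 1 − 0.05/0.295 = 0.83 in men.

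**Time series.** If f is constant over time, a true absolute change in level is measured as f times that change; at f = 0.5 it is halved.

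**VTE.** The abstract and 9.3.2 make VTE a contraindication. The abstract (which names cardiovascular death), section 8 and 9.9 restrict the comparison to people without contraindications. Section 9.2.5.3 applies the VTE exclusion to one endpoint. These statements cannot all hold for MI and cardiovascular death.

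**The case against.** **A fixed window gives equal ascertainment.** RMM effectiveness is judged on level and slope over calendar time. Only one year of prior data is guaranteed (9.2.1), SIDIAP data begin in 2005 (9.2.2), and THIN follow-up averages 5.5 years (9.4.3). With an any-history rule, look-back lengthens over the series, so recorded history can rise without any change in prescribing, and differently by database. This stands. It is a reason to report the fixed-window series as well, but it does not make a one-year count a measure of the restriction.

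**The window on the IHD line might attach only to nitrate use.** That is possible for IHD, but the PAD, TIA/stroke and VTE lines leave no such reading.

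**The VTE omission may be deliberate.** Section 9.2.5.3 speaks of the new contraindications, and 7.2 calls VTE an already recognized risk. This may explain the list, but it does not reconcile it with the abstract, 9.3.2 and 9.9.

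**Stronger readings that the documents do not support.**

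- A reader might infer that the one-year rule leaves many patients with older cardiovascular disease in the comparative cohort, where they would supply a sizeable part of the MI cases. Section 9.2.5.3 has its own exclusion without a window, and nothing says that 9.3.2 overrides it.
- A reader might also infer that prior VTE is more common among bisphosphonate users and so biases the cardiovascular-death comparison. The protocol gives no figure for this, and anticoagulant use in the prior year is among the candidate confounders (9.3.4).

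**Conclusion.** The point holds for the prevalence of contraindicated SR use and for the strata by number of contraindications: as written, 9.3.2 applies a narrower criterion than the restriction it is meant to evaluate. The direction of the bias is certain, because a one-year count cannot exceed an any-history count. The size is not known. The ranges of about 6-13% (women) and 9-21% (men) rest on two assumptions: that the planning figures are any-history values, and that 30-70% of patients with a history have a record in the last year, taken as one share for all conditions. Nitrate use and history codes entered within the year would raise that share.

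The VTE inconsistency is a textual contradiction that needs no assumption. Its effect on the MI and cardiovascular-death estimates cannot be sized from the protocol.

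The sample size is not threatened: a lower measured prevalence needs fewer users for the same precision (at f = 0.5, 194 men and 134 women).

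**What to change.** 1. In 9.3.2, for the prevalence estimates and the strata, define IHD, PAD, TIA/stroke and VTE as any record on or before the assessment date, including the starred history codes in Appendix 14.3.2. Anchoring on an assessment date also serves prevalent users, whose SR start is unknown. Leave the uncontrolled-hypertension rule as it is.
2. Refer 9.2.5.3 to that definition, so that one concept has one rule.
3. Report the interrupted time series under both the any-history and the fixed one-year look-back, and state why.
4. Reconcile 9.2.5.3 with the abstract, 9.3.2 and 9.9 by applying the prior-VTE exclusion to all three endpoints in both arms.

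The cost is protocol wording, one look-back parameter at extraction and a second run of the time series. The small downside is that available look-back differs by database and grows over calendar time, which the parallel fixed-window series makes visible. The cohort for the MI and cardiovascular-death comparisons becomes slightly smaller.

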### 9.4.4. Aarhus Database

The Aarhus University Prescription database comprises clinical and prescription data on the population of former North-Jutland, Aarhus, Rinkjebing and Viborg counties, which since 2007 are called the Central Denmark Region and the North Denmark Region. This population covers a total of 1.8 million inhabitants and is representative of the population of Denmark (Ehrenstein, 2010). Data available on these subjects comprise their eligibility, dispensing data, hospitalizations and procedures and the population can also be linked to other National Danish registries. Dispensing data comprise the filled prescriptions for all ambulatory patients and contains information on name of the drug, ATC code, package identifier (strength and route of administration), and the date of refill. These data can be linked to the national registry of patients that comprises information on admissions to Danish somatic hospitals, emergency rooms and outpatient clinics, diagnosis codes and procedures are registered. These databases have been used in numerous studies and are proven valid for pharmaco-epidemiological research (Ehrenstein, 2010). The study must be announced at the governance committee.

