### 9.6.6. Missing data

Since the underlying data represent attended medical care we assume that absence of information of clinical events means absence of that condition. Lack of information on smoking, and alcohol use may occur, but this is unlikely differential.

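### Uncontrolled hypertension: unmeasured and untreated users count as negative, so the time series cannot separate a change in blood pressure recording from a change in prevalence

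*Protocol*

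**What the plan says.** Section 9.3.2 defines the criterion as a conjunction: "Uncontrolled hypertension, defined by MAH as the combination of the following: 1.previous diagnosis of hypertension coded in electronic medical records"; then "2.documented use of any anti-hypertensive therapy (either at that time or in the previous year before SR therapy initiation"; and third "at least two readings of Systolic Blood Pressure" at or above 150, or diastolic at or above 95, "mmHg recorded in the 3 months prior to SR therapy initiation". Section 9.2.5.3 uses the same rule to exclude patients from the comparative safety study: "a patient will be defined as 'uncontrolled hypertension' if the 3 following conditions apply", the second being "There is documented use of any anti-hypertensive therapy (either at that time or in the previous year before SR/BP initiation".

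Neither section says how to classify a user with too few readings, and neither makes the criterion conditional on readings being available. The general rule in 9.6.6 is that "we assume that absence of information of clinical events means absence of that condition".

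For Aarhus, 9.4.4 states: "Data available on these subjects comprise their eligibility, dispensing data, hospitalizations and procedures". Table (9.4) 1 classes that database as administrative. Section 9.4.5, by contrast, names blood pressure measurements among the SIDIAP variables.

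Section 9.7.2.2 estimates the prevalence of each contraindication by period and country. It follows each one monthly with segmented regression, separately for incident and prevalent users, with every database serving as its own control. Section 9.7.4 pools all estimates across databases.

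**The concern.** A negative on this criterion can mean that blood pressure was controlled, that it was not recorded twice, that the patient was diagnosed but untreated, or that the database holds no readings. The recorded proportion is therefore true prevalence multiplied by the chance that a truly uncontrolled user is captured by all three conditions.

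Stable under-capture lowers the level but leaves a before/after comparison usable in relative terms. Capture that changes at the intervention does not. The first DHPC made uncontrolled hypertension a contraindication, so it is plausible that blood pressure was recorded more often before SR was started after May 2013. A series with no external control would show that as a level or slope change in the contraindication, which is the quantity 9.7.2.2 uses to judge the risk minimisation measures.

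The same classification decides who enters the comparative safety cohort as free of contraindications.

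**Working it through.** **The plan's own figures.** The protocol gives no prevalence, study size or power for uncontrolled hypertension. The nearest figures are those in 9.5.1, n = 1.96² × p(1 − p) / 0.05². For p = 29.5%, 19.2% and 53.1% this gives 319.6, 238.4 and 382.7, so the stated 320, 239 and 383 reproduce. None of them involves hypertension.

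**What the rule returns (9.3.2, 9.2.5.3).**
- Coded, treated, two high readings in 3 months: positive.
- Coded, treated, one high reading or none recorded: negative.
- Coded, two high readings, no antihypertensive record: negative.
- No coded diagnosis, whatever the readings: negative.
- Database without readings: every user negative.

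These are negatives on this criterion only. The same user may be positive on another contraindication, and the other contraindications are estimated separately.

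**Size of the Aarhus zero (Table (9.5) 1).** Incident users: 46/5,819 = 0.8%. Prevalent users: 464/27,764 = 1.7%. If databases were weighted by 2012 incident users, the zero would multiply the pooled proportion by (5,819 − 46)/5,819 = 0.992. The pooled distortion is small on that weighting, but the Danish figure itself would be meaningless.

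**How strongly capture depends on measurement (assumed rates).** If readings follow a Poisson process, P(at least two in 3 months) = 1 − e^(−λ)(1 + λ), with λ the yearly rate divided by 4. At 2, 4, 8 and 12 readings a year this is 9%, 26%, 59% and 80%.

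**Effect of changing capture among new starters (all inputs assumed).** Let π be true prevalence, m0 and m1 the share of truly uncontrolled patients captured before and after, and r the share of detected patients not started on SR.
- Recorded before = π·m0.
- Recorded after = π·m1(1 − r) / (1 − π·m1·r).

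With π = 10%, m0 = 30% and m1 = 50%, recorded prevalence before is 3.0%. Afterwards:
- r = 0: 5.0%, with true prevalence unchanged.
- r = 0.2: 0.040/0.990 = 4.04%, while true prevalence among starters falls to 0.090/0.990 = 9.1%.
- r = 0.4: 3.06%.
- r = 0.6: 2.06%.

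The apparent rise ends at r = (m1 − m0)/(m1 − m0·π·m1) = 0.20/0.485 = 0.41. Over π = 5%, 10% and 20%, with capture going from 30% to 50%, 30% to 70% or 50% to 80%, this threshold lies between about 0.39 and 0.61. Recorded prevalence can therefore rise, stay flat or fall.

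**Would a measured-only denominator solve it? (assumed inputs)** Hold true prevalence at 15%. Suppose 40% of uncontrolled and 10% of controlled users have two readings before, and 50% and 30% after.
- Before: 0.15 × 0.40 = 0.060; 0.85 × 0.10 = 0.085; 0.060/0.145 = 41%.
- After: 0.15 × 0.50 = 0.075; 0.85 × 0.30 = 0.255; 0.075/0.330 = 23%.

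Prevalence in the subgroup nearly halves with no true change, so this denominator can mislead in the opposite direction.

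**The case against.** The rule is a declared choice. Both sections attribute it to the MAH, they agree with each other, and 9.2.5.3 calls it an operational definition. A reader might infer that the treatment condition is an error to be deleted. The documents do not support that: whether an untreated patient with high readings falls under the label term is a clinical matter they leave open. This part of the objection stands.

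A reader might also infer that the DHPC will make prevalence appear to rise. No section says it changed blood pressure recording. The direction depends on how many detected patients are not started, and only users who initiate after May 2013 could be affected. This stands too.

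A third inference is that the comparative safety result is biased. The same rule applies to SR and bisphosphonate initiators, and 9.3.4 lists hypertension diagnosis and antihypertensive use as covariates. Blood pressure level is not listed, so untreated patients with high readings cannot be told apart from untreated patients with normal ones. Even so, no differential error is shown.

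On Aarhus, 9.4.4 adds that linkage to other national registries is possible, results are shown by country, and 9.6.4 benchmarks rates. A zero would probably be noticed, but the protocol does not say it would be treated as missing.

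Finally, 9.9 already admits underestimation of contraindications, and details are deferred to the SAP. But 9.9 does not address capture that changes over time. The classification is fixed in the protocol, without the availability qualifier that 9.3.4 gives alcohol and smoking, or that 9.3.2 gives the fracture-risk tool.

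**Conclusion.** The point holds as a limit on what this one component can show. By the text, unmeasured users and diagnosed untreated users are negative, and a database without readings yields a structural zero that enters the by-country and pooled results. The time series cannot distinguish a change in recording at the DHPC from a change in true prevalence.

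Its practical size is unknown, because the protocol gives no measurement frequency. The figures above illustrate the mechanism and do not forecast the result. That Aarhus lacks readings is inferred from its description, and its weight is small. That recording changed after May 2013 is an inference from the content of the DHPC. The evidence supports additional outputs. It does not support replacing the definition or the main denominator.

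**What to change.** Keep the MAH definition and the all-user denominator as the main analysis. In 9.3.2 and 9.7.2.2 add:

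1. In any database without blood pressure readings, this component is reported as not assessable and that database is left out of its pooled estimate. Confirm availability for each database before extraction.
2. The monthly share of SR initiators with at least two readings in the 3-month window is shown beside the series.
3. Two sensitivity analyses: (a) the series among users with at least two readings, stating that selection into this subgroup may itself change over time; (b) a classification without the antihypertensive-use condition, with treated and untreated patients shown separately. Repeat (b) for the exclusion in 9.2.5.3.

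The sensitivity versions concern study classification only and imply nothing about the clinical definition. The cost is short wording in three sections and a few extra outputs from data already extracted. The downside is that the measured-only series is smaller and selected.
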